#### Hypothesis for Aim 1:

1.1 – After starting Omegaven® on PN, the rate of fatty acid deficiencies and imbalances will be as low as before Omegaven®. Also, the rate of triglyceride events > 400 mg/dL with Omegaven® will be similar to that seen with PN administered with soy oil IFE (conventional emulsion, i.e., Intralipid®).

1.2 – PN containing Omegaven® will be safe for patients with respect to the risk of unexpected bleeding, coagulopathies, and other adverse events.

[name], Department of Surgery, Children's Hospital & Medical Center  
[name], Department of Surgery, Children's Hospital & Medical Center  
[name], Pediatric Research Office, Dept. of Pediatrics, UNMC  
[name], Department of Biostatistics, College of Public Health, UNMC

1.3 – PN containing Omegaven® will promote more short-term growth and development than conventional fat emulsions.

2. To determine if established PN associated liver disease can be reversed or its progression halted by using a parenteral fat emulsion prepared from fish oil as measured by normalization of serum levels of hepatic enzymes and bilirubin.

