**Hypothesis for Aim 2:**

2.1 – Our primary hypothesis is that, after reaching bilirubin levels  $> 2$  mg/dL, patients receiving Omegaven® will reach a bilirubin level  $\leq 2$  mg/dL faster than patients receiving conventional fat emulsions. Additionally, while patients receiving Omegaven® will experience a decrease in their levels of bilirubin and other hepatic enzymes over time, patients receiving conventional emulsions will maintain high levels of bilirubin and other hepatic enzymes over time.

2.2 – Patients with surgical gastrointestinal disease and cholestasis will have better clinical hepatic outcomes than patients receiving conventional emulsions.

2.3 – Since patients receiving Omegaven® will have improved immune function, they will have a lower infection rate than patients receiving conventional fat emulsions.

2.4 – Due to a better general hepatic condition, patients receiving Omegaven® will also experience lower occurrence of liver transplant, death from hepatic associated causes, and blood transfusions.

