### Outcome/Endpoints

#### *Treatment safety*

Our primary outcome for treatment safety will be based on patient's essential fatty acid profile. We will compare patients before treatment with Omegaven® started and after treatment started (one month after treatment started until treatment stopped) with respect to the frequency with which triene/tetraene ratio  $> 0.2$  at any time. Primary analyses for these and all other safety outcomes will be based on a follow-up time for Omegaven® starting 30 days after baseline, i.e., 30 days after treatment started for Omegaven® patients and 2 months after the first direct bilirubin level  $< 2$  mg/dL was recorded.

Additional comparisons across treatment periods for subjects receiving Omegaven® will be aimed to assess occurrence of spontaneous bleeding (e.g., unexplained bruising, oozing from gums/incision sites), and maximum triene/tetraene ratio, minimum platelets, maximum international normalized ratio (INR), and trends in pre-albumin (age standardized levels). We will also explore trends in coagulopathies based on curves of platelets, prothrombin time (PT), partial thromboplastin time (PTT) over time, and INR. We will also describe the rate with which INR ratios were  $> 2$  (number of days/follow-up time), as a marker of coagulopathies.

Additional evaluation of Omegaven® will be performed with regards to rate in which albumin is  $> 3$  g/dL, maximum triglyceride level, rate of blood stream infections (number of positive blood cultures/follow-up-time under PN after baseline), rate of central venous catheter (CVC) infections (number of CVC infections/follow-up time and number of gram positive CVC infections/follow-up time), and occurrence of anaphylactic reactions after baseline.

We will describe trends over time for all outcomes associated with fatty acid profiles (including triene/tetraene ratios, triglycerides, total omega-6 fatty acids, total omega-3 fatty acids, total saturated, total monounsaturated, and total polysaturated fatty acids). Specific fatty acids such as arachidonic, palmoleic, palmitic, oleic, stearic, and linoleic fatty acids will also be evaluated and described.

[name], Department of Surgery, Children's Hospital & Medical Center  
[name], Department of Surgery, Children's Hospital & Medical Center  
[name], Pediatric Research Office, Dept. of Pediatrics, UNMC  
[name], Department of Biostatistics, College of Public Health, UNMC

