#### **G. Adverse Event Criteria and Reporting Procedures**

Adverse events (AEs) will be assessed and reported from the time of the first Omegaven® infusion until exit from the study in accordance with UNMC Pediatric IRB reporting requirements. In particular, the patient will be observed during and shortly after Omegaven® administration for the occurrence of anaphylactic or allergic reactions. Other expected adverse events include death, blood stream infection; transfer to ICU for treatment of respiratory distress or hemodynamic instability; re-hospitalization for treatment of blood stream infection, dehydration, electrolyte abnormalities, catheter malfunctions, bowel obstructions, and urinary tract infection. Unexpected adverse events will also be assessed and reported in compliance with the UNMC Pediatric IRB requirements. Patients experiencing any adverse events that are moderate or severe in nature and that may be related to Omegaven® will have their treatment temporarily halted until the adverse event has resolved. Dose modifications will occur as described above. If a dose reduction is made for adverse events later considered to be unrelated to Omegaven®, the Omegaven® dose will be increased back to the dose prescribed prior to the dose reduction. Patients with anaphylactic or allergic reactions will not continue Omegaven® treatment.

Any serious or unsuspected adverse events will be reported to the IRB and the FDA within 72 hours of the occurrence being known, or immediately if the event is fatal or life threatening as per UNMC Pediatric IRB Policy on Adverse and Unexpected Events and Unanticipated Risks to Research Subjects and Others. This will be done in person, by telephone, or email, and by completion of the IRB's form for adverse/unexpected event reporting.

Adverse events are detected by Children's Hospital & Medical Center acute care medical and nursing staff during provision of standard care services including the routine monitoring of vital signs and daily physical exam data. Adverse events identified by Children's Hospital & Medical Center staff are reported to the Principal Investigator immediately by telephone or pager, and subsequently to the appropriate board or committee.

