#### **Safety Labs Schedule:**

Lab Name	Schedule*
Serum triglycerides	At baseline, weekly for 4 weeks, monthly thereafter
Coagulation labs	At baseline, weekly until direct bilirubin is < 2mg/dL, monthly thereafter
Fatty acid profile	At baseline, monthly thereafter

\*minimum requirements, may be performed more frequently for routine clinical care

If under the discretion of the principal investigator the patient is able to return home and receive Omegaven®, the patient is required to return to Children's Hospital & Medical Center every 2 months or other mutually agreed upon schedule for evaluation and follow up. The Principle Investigator also requires for arrangements to be made through the patient's home health care agency for the required weekly or monthly blood draws the patient will need while at home in order to remain on Omegaven®. The lab results then must be faxed to Children's Hospital & Medical Center in a timely manner. Additionally, measures will be taken to decrease the chance of administration errors when Omegaven® is given in the home. Families will be provided with a letter outlining strategies for reducing medication administration errors, such as independent double-checks.

Dose reduction will occur if there is evidence of lipid intolerance (serum triglycerides  $>$  200mg/dL) or evidence of bleeding. Growth indices include weight, length, and head circumference will also be monitored.

Other standard care laboratory results will be captured for the Omegaven® protocol. These are listed along with the standard schedule in Table 3.

The frequency of laboratory monitoring may be reduced to monthly or as clinically necessary, for patients who have been on a stable regimen of Omegaven® for a minimum of 4 months and whose serum bilirubin and hepatic enzymes have normalized.

The study team will round on all inpatients receiving Omegaven® therapy. A complete comprehensive case review for all inpatients receiving Omegaven® therapy under the compassionate-use protocol and any outpatients issues will be discussed among [name], [name], and the study coordinator. All pertinent medical, nutritional, and psychosocial outpatient information will be reviewed during these case reviews.

[name], Department of Surgery, Children's Hospital & Medical Center  
[name], Department of Surgery, Children's Hospital & Medical Center  
[name], Pediatric Research Office, Dept. of Pediatrics, UNMC  

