**Side effects:**

The infusion of Omegaven® can lead to a prolonged bleeding time and an inhibited platelet aggregation. In rare cases, patients may experience a fishy taste.

The administration of Omegaven® should be stopped or reduced if there is a marked increase in blood glucose levels during the Omegaven® infusion. Undesirable effects that are seen during the infusion of Omegaven® that may also occur with conventional fat emulsions (i.e. Intralipid®) include:

Slight rise in body temperature  
Heat sensation and/or cold sensation  
Chills  
Flushing or cyanosis  
Lack of appetite, nausea, vomiting  
Dyspnea  
Headache, pain in the chest, bone pain  
Priapism  
Increase/decrease in blood pressure  
Anaphylactic reactions/erythema

Other expected adverse events that are common to all patients with short bowel syndrome, regardless of the type of fat emulsion they receive, include blood stream infections and re-admittance to hospital. Causes for re-hospitalization include dehydration, bloodstream infections, electrolyte abnormalities, bowel obstruction, and central venous catheter malfunction.

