**Summary – Overall Risk Assessment**

Patients will be at some risk inherent in taking a pharmaceutical agent that has not been fully evaluated for long duration treatment. However, the availability of safety data demonstrates no life-threatening risks or toxicities to vital organs or physiologic functions. Prolonged bleeding times and inhibition of platelet aggregation are a potential risk, especially to those patients with an underlying coagulopathy or those being treated with an anticoagulant. The potential benefits

[name], Department of Surgery, Children's Hospital & Medical Center  
[name], Department of Surgery, Children's Hospital & Medical Center  
[name], Pediatric Research Office, Dept. of Pediatrics, UNMC  
[name], Department of Biostatistics, College of Public Health, UNMC

of Omegaven® in this patient population are mainly based on the experimental evidence. However, the study will only be available to those for whom no standard therapy is available or appropriate, or has already failed. The risks and potential benefits will require careful individual assessment by both the investigators and patients. The heterogeneity of clinical manifestations will lead to non-uniform risk-benefit ratios across the eligible patient population.

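### The one named bleeding outcome, spontaneous bleeding, is narrower than the drug's listed hazard and the bleeding rule for dose reduction, so triggered bleeds can miss the before/after comparison

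*Protocol*

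**What the plan says.** All references are to the protocol.

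- **Hypothesis for Aim 1, item 1.2:** treatment will be "safe for patients with respect to the risk of unexpected bleeding, coagulopathies, and other adverse events".
- **Section D, Treatment safety:** among the additional comparisons across treatment periods is "occurrence of spontaneous bleeding (e.g., unexplained bruising, oozing from gums/incision sites" (the parenthesis closes there). No other clinical bleeding outcome is named. Analysis of Safety and Tolerability names INR, platelets, PT and PTT, but no clinical bleeding.
- **Side effects:** "The infusion of Omegaven® can lead to a prolonged bleeding time and an inhibited platelet aggregation". The Summary – Overall Risk Assessment adds: "Prolonged bleeding times and inhibition of platelet aggregation are a potential risk, especially to those patients with an underlying coagulopathy".
- **Safety Labs Schedule:** the dose will be reduced for raised triglycerides "or evidence of bleeding", with no qualifier on the kind or cause of the bleed.
- **Section G:** "Adverse events (AEs) will be assessed and reported from the time of the first Omegaven® infusion until exit from the study".
- **Hypothesis for Aim 2, item 2.4:** treated children are expected to have "lower occurrence of liver transplant, death from hepatic associated causes, and blood transfusions". Analysis of Efficacy also uses red-cell transfusions as a predictor of laboratory spikes. Neither safety list mentions transfusions.

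**The concern.** If haemostasis is impaired, bleeding from an operation, a catheter site or a gut lesion can be longer or heavier. Bleeding may also appear without a trigger. The children in this study are surgical patients with intravenous access, so triggered bleeds are plausible, and the word *spontaneous* tends to leave them out. The study is open-label, so staff who know the treatment decide which bleeds qualify.

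What is at stake is the reading of hypothesis 1.2. A low count of spontaneous bleeds could be taken as reassurance about the drug's named hazard, while bleeds serious enough to change the dose appear only among general adverse events, with no pre-treatment figure beside them.

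**Working it through.** The protocol gives no bleeding rate and no calculation for this outcome, so there is no figure to reproduce. The check is mainly textual.

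**Step 1. Compare the scope of each statement.**

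| Place in protocol | Scope of bleeding | Before treatment? | On treatment? |
|---|---|---|---|
| Hypothesis 1.2 | Unexpected bleeding, plus coagulopathies and other adverse events | Not stated | Yes |
| Treatment safety outcome | Spontaneous bleeding, with examples | Yes (comparison across periods) | Yes |
| Safety Labs Schedule, dose reduction | Bleeding, unqualified | No | Yes |
| Section G, adverse events | Any adverse event | No (starts at first infusion) | Yes |

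Only the Treatment safety outcome covers both periods, and its bleeding definition is narrower than the dose-reduction rule or the adverse event net.

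**Step 2. Follow one triggered bleed.** Take a child on treatment who bleeds from a catheter site in a way nobody would call spontaneous. The dose-reduction rule applies and an adverse event is recorded. The bleeding outcome need not count it. The same bleed a month before treatment is neither in that outcome nor in the adverse event records. A reader therefore cannot rebuild a before/after comparison of all bleeding from what the protocol plans.

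**Step 3. Is the definition clear at its edge?** One example given for spontaneous bleeding is oozing from incision sites. An incision is a local trigger, so two abstractors could reasonably classify the same post-operative ooze differently.

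**Step 4. Do the laboratory outcomes fill the gap?** The Reversal Study Lab Schedule and Tables 2 and 3 provide for PT, PTT, INR, fibrinogen and platelet counts (Table 2 only as coagulation labs). INR, PT and PTT reflect clotting factors, and a platelet count says nothing about platelet function. No bleeding time or aggregation test is scheduled. Clinical bleeding is thus the main planned signal for the platelet effect.

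**Step 5. Illustrate the size (assumptions only).** Inputs: n = 30, the largest size in Table 4; p, the share of children with any bleed, 10% to 30% (assumed); s, the share of those bleeds with a trigger and not counted, 25% to 75% (assumed); one bleed per child.

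Children uncounted = n × p × s

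- Low: 30 × 0.10 × 0.25 = 0.75, about 0.8
- Middle: 30 × 0.20 × 0.50 = 3, so 3/30 = 10% is observed instead of 6/30 = 20%
- High: 30 × 0.30 × 0.75 = 6.75, about 6.8

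As a more extreme case, let 6 of 30 children bleed. With exact (Clopper-Pearson) 95% intervals:

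| Bleeds counted | Observed | 95% interval |
|---|---|---|
| 6 (all) | 20% | 7.7% to 38.6% |
| 1 (five judged triggered) | 3.3% | 0.1% to 17.2% |
| 0 (all judged triggered) | 0% | 0% to 11.6% |

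The before/after difference shrinks too. If 10% bleed before and 30% on treatment, and half the bleeds in each period go uncounted, the difference falls from 30% − 10% = 20 points to 15% − 5% = 10 points. If the uncounted share differs between periods, the distortion could go either way.

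**The case against.** A reader might infer that triggered bleeding disappears from the safety result altogether. The documents do not support that.

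- Hypothesis 1.2 also covers coagulopathies and other adverse events, so a triggered bleed on treatment still falls within it.
- In the outcome definition, *unexplained* qualifies bruising only, within a list of examples. Incision-site oozing is included, and no section says that a bleed with a trigger is excluded.
- On-treatment bleeds are reportable under section G. All adverse events are classified for relatedness, the investigators review them at least monthly, and the DSMB chair receives the reports.
- The listed effect is prolonged bleeding *time*, not prolonged bleeding as an event.
- Bleeding is an additional comparison, not a primary outcome, and the primary safety analysis is descriptive.
- In a before/after design, counting every procedural bleed mixes any drug effect with the timing of operations. A focus on spontaneous bleeding gives up sensitivity to gain specificity.
- A dose rule that is wider than an analysed outcome is not in itself a contradiction.

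All of this stands and limits the point. Two answers remain. Adverse event records cannot supply the pre-treatment half of the planned comparison. The specificity argument is a reason to report spontaneous bleeding separately, which the fix does; it is not a reason to count nothing else. Transfusions do appear under hypothesis 2.4, but as a hoped-for benefit rather than in a safety summary.

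**Conclusion.** The concern holds in a limited form. The named bleeding outcome is narrower than the hazard the protocol lists and narrower than its own trigger for reducing the dose, and its incision-site example blurs the definition. A bleed can change treatment without entering the planned comparison of periods. It does not vanish from the study, because on treatment it remains an adverse event.

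The size is unknown. The range of about 0.8 to 6.8 children in 30 rests entirely on assumed bleeding rates and assumed trigger shares. If no bleed had a trigger, or if abstractors read the definition broadly, nothing would be lost. This is an inexpensive improvement to an outcome definition and does not by itself invalidate the safety analysis.

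**What to change.** Reconcile hypothesis 1.2, the Treatment safety outcome and the Safety Labs Schedule as follows.

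1. Define the bleeding outcome as any clinically evident bleeding, whatever its cause or expectedness, including gastrointestinal, procedural and catheter-site bleeding.
2. Abstract it from the charts by the same rule in the pre-treatment and treatment periods.
3. Report two subsets: spontaneous bleeding, with a definition that settles where incision-site oozing belongs, and bleeds that led to a dose reduction. The second subset exists only on treatment.
4. List the transfusion data already needed for hypothesis 2.4 and the efficacy analysis in the safety summaries as well.

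The cost is endpoint wording and some extra abstraction from charts that section E already has reviewed. For children referred from elsewhere, the pre-treatment part may need outside records, but the existing outcome needs those too. The downside is a higher overall bleeding rate that includes some bleeding unrelated to the drug; the spontaneous subset keeps that distinction visible. The change concerns counting only and leaves every dose and clinical rule as written.

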**Hypothesis for Aim 2:**

2.1 – Our primary hypothesis is that, after reaching bilirubin levels  $> 2$  mg/dL, patients receiving Omegaven® will reach a bilirubin level  $\leq 2$  mg/dL faster than patients receiving conventional fat emulsions. Additionally, while patients receiving Omegaven® will experience a decrease in their levels of bilirubin and other hepatic enzymes over time, patients receiving conventional emulsions will maintain high levels of bilirubin and other hepatic enzymes over time.

2.2 – Patients with surgical gastrointestinal disease and cholestasis will have better clinical hepatic outcomes than patients receiving conventional emulsions.

2.3 – Since patients receiving Omegaven® will have improved immune function, they will have a lower infection rate than patients receiving conventional fat emulsions.

2.4 – Due to a better general hepatic condition, patients receiving Omegaven® will also experience lower occurrence of liver transplant, death from hepatic associated causes, and blood transfusions.

**BACKGROUND**

*Parenteral Nutrition Associated Liver Disease (PNALD)*

Parenteral nutrition (PN) provides intravenous nutritional supplementation for patients unable to absorb adequate enteral nutrients secondary to insufficient intestinal length or function. PN contains the macronutrient building blocks of the human diet in their most elemental forms (amino acids and dextrose) and is commonly administered with a fat emulsion to avoid essential fatty acid deficiency and to provide a calorically dense source of non-protein calories. In addition, PN contains the essential micronutrients (electrolytes, trace elements, and vitamins) to provide an optimal nutritional regimen. Before the development of PN in the late 1960's, patients with insufficient gastrointestinal absorptive function commonly died of starvation and subsequent complications of malnutrition(1, 2). Today, more than 30,000 patients are permanently dependent on parenteral nutrition for survival. However, PN continues to be associated with hepatic injury that occurs at an unpredictable rate and includes both biochemical, i.e., elevated serum aminotransferase and alkaline phosphatase, and histologic alterations such as steatosis, steatohepatitis, lipidosis, cholestasis, fibrosis, and cirrhosis (3, 4). These abnormalities, which may worsen with the duration of PN administration, is more prevalent in the pediatric population. Additional risk factors for this condition include prematurity, low birth weight, long-term use of PN, the lack of concomitant enteral intake, sepsis, and multiple operative procedures (5).

Although the pathological features of PNALD have been well described, the etiology, prevention, and treatment of this complication are not well understood. Multiple hypotheses exist to explain the pathogenesis of PNALD including altered gut hormonal profiles (6), the propensity for bacterial translocation in the absence of enteral intake (7, 8), intestinal stasis resulting in the reduced clearance of hepatotoxic bile acids (8), and direct deficiencies or toxic components of the PN solution itself resulting in excessive glucose calorie uptake, excessive lipid infusion, or nutritional deficiencies such as essential fatty acid deficiency (9-11). None of these theories has been confirmed consistently. The etiology of PNALD is currently considered

[name], Department of Surgery, Children's Hospital & Medical Center  
[name], Department of Surgery, Children's Hospital & Medical Center  
[name], Pediatric Research Office, Dept. of Pediatrics, UNMC  
[name], Department of Biostatistics, College of Public Health, UNMC

multifactorial. Available treatment options for this disease process are limited and have achieved moderate success at best. Care of the PN-dependent patient is focused on gradually increasing enteral caloric intake as the residual bowel adapts allowing PN to be discontinued (12). In fact, it has been shown both experimentally and clinically that partial enteral nutrition, when tolerated, helps to protect against the development of PNALD (13-15). In severe cases of refractory hepatic failure, liver transplantation with or without accompanying small bowel transplantation remains the only treatment option.

